For this protocol, the following “Just in time” human subjects protection training courses are required for investigators and staff:

(Per SOP 25, PIs or IRBs require investigators and staff working on a protocol to complete the following training, as applicable. Delete those that are not applicable. Indicate “None” if no training beyond the general training is required.)

- NIAID GCP course
- CITI GCP modules

Total requested accrual = 184 Healthy Volunteers

| | | |
|----------------------------------|--|------------------------------|
| Project Uses Ionizing Radiation |  No |  Yes |
| IND/IDE |  No |  Yes |
| Durable Power of Attorney |  No |  Yes |
| Multi-institutional Project |  No |  Yes |
| Data and Safety Monitoring Board |  No |  Yes |
| Technology Transfer Agreement |  No |  Yes |
| Samples are being stored |  No |  Yes |

Flesch-Kincaid reading level of consent form:

Healthy Volunteer: 7.8

Précis:

Objective: To determine the effect of non-invasive brain stimulation on anxiety and anxiety-cognition interactions in healthy subjects. Toward this aim we will test the effect of transcranial magnetic stimulation (TMS) on two outcome measures: 1) Fear and anxiety during the threat of predictable and unpredictable shock (NPU threat test), and 2) Working memory (WM) related anxiety downregulation while performing the Sternberg WM task under threat of shock.

Study population: The study population will consist of up to 184 healthy volunteers between the ages of 18-50.

Design: This study will consist of two (sub-studies 1 and 2) or three (sub-study 3) outpatient visits (1 MRI, 1 or 2 TMS visits [2 for sub-study 3]). In this protocol we will explore the effect of TMS in three sub-studies in the TMS study visit. The sub-studies will contain either the NPU or the Sternberg task during the TMS visits. The first visit (MRI) will consist of the same procedures for all sub-studies. Each subject will be assigned to only one of the sub-studies.

Sternberg Task: Expose subjects to active or sham TMS to a region of the frontoparietal attention network during the Sternberg WM task. Subjects will have to maintain a series of letters in WM for a brief interval during blocks of safety and threat of shock.

NPU Task: Expose subjects to active or sham TMS to a region of the frontoparietal attention network during the NPU threat test. Subjects will be exposed to blocks in which they are either 1) safe from shock (neutral), 2) at risk of shock delivered only during a cue (predictable), or 3) at risk of shock presented randomly (unpredictable).

Outcome measures: In both studies the primary outcome measure will be anxiety-potentiated startle (APS), which is the increase in startle magnitude during periods of threat compared to periods of safety. We expect active, but not sham TMS to increase activity in the dlPFC, and therefore reduce APS in both studies.

Table of Contents

| | |
|---|-----------|
| 1. Introduction and Background | 9 |
| a. Background | 9 |
| b. Significance | 11 |
| c. Preliminary data | 11 |
| 2. Study Objectives | 17 |
| a. Primary objectives | 17 |
| 3. Subjects | 18 |
| a. Description of study populations | 18 |
| b. Inclusion criteria | 18 |
| c. Exclusion criteria | 18 |
| 4. Study Design and Methods | 19 |
| a. Study overview | 19 |
| b. Recruitment | 20 |
| c. Screening | 21 |
| d. Study procedures | 22 |
| e. End of participation | 27 |
| 5. Management of Data and Samples | 27 |
| a. Storage | 27 |
| b. Data sharing plan | 28 |
| 6. Additional Considerations | 28 |
| a. Research with investigational drugs or devices | 28 |
| b. Gene therapy | 28 |
| 7. Risks and Discomforts | 28 |
| a. Procedures | 28 |
| b. Procedures to Minimize Risks | 31 |
| 8. Subject Safety Monitoring | 32 |
| 9. Outcome Measures | 33 |
| a. Primary outcome measures | 33 |
| 10. Statistical Analysis | 33 |
| a. Analysis of data/ study outcomes | 33 |
| b. Power analysis | 33 |
| 11. Human Subjects Protection | 34 |
| a. Subject selection | 34 |
| Justification for exclusion of children | 34 |
| Justification for inclusion of other vulnerable subjects | 34 |
| Justification for exclusion of other vulnerable subjects | 34 |
| Justification for exclusion of non-English speaking subjects | 35 |
| Justification for exclusion of subjects over 50 years of aged | 35 |
| Justification for exclusion of non-right-handed subjects | 35 |

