One variant of the threat of shock paradigm is the so-called NPU paradigm, where subjects are exposed to simple cues during blocks of no threat (N), predictable threat (P), and unpredictable threat (U) (Schmitz and [name], 2012). During this paradigm, simple geometric shapes serve as cues (presented for 8 s). During the predictable threat blocks, these cues indicate that a shock may occur, while during the unpredictable and neutral blocks, these cues are not predictive of the shock. During the no threat blocks subjects are instructed that they are completely safe from shocks, and during the unpredictable blocks, subjects are instructed that they could receive a shock at any point. This paradigm provides measures of fear (e.g., fear-potentiated startle) associated with the threat cue in the P condition and of anxiety (e.g., anxiety-potentiated startle) in the N, P, and U contexts (no-cue periods). This paradigm is ideal to test the top-down inhibition hypothesis because it allows for the testing of both fear and anxiety, without adding additional cognitive demands. In addition, cue presentations during the NPU task activate the dlPFC (See below), which may reflect an implicit form of top-down emotion regulation.

The purpose of this protocol is to use TMS to determine the role of the FPN in anxiety reduction. According to our model, we have 2 hypotheses. First, suppressing activity in

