There will be 4, 14 min runs of the experiment (2 active and 2 sham). Within each run, there will be 8 blocks (2 predictable, 2 unpredictable, 4 neutral). There are twice the number of neutral blocks to ensure that safe blocks alternate with threat (predictable or unpredictable) blocks. During half of the blocks (1 predictable, 1 unpredictable, 2 neutral), subjects will receive a continuous train of 1 Hz stimulation to the left IPS. Within each block, there will be 2 types of trials based on the delivery of startle probes. Startle probes will be presented either during the cue period, or the ITI. During the predictable and unpredictable blocks, there will be 4 trials per condition. Given that there will be twice as many neutral blocks, during these blocks there will only be 1 trial per condition. The result will be a total of 192 trials across the entire experiment (2 [active vs. sham] x 2 [neutral vs. predictable vs. unpredictable] x 2 [maintenance vs. ITI] x 2 [TMS vs. no TMS] x 2 [run repetitions] x 4 [block*trial repetitions]). Trials will last approximately 17 seconds. There will be a total of 3 shocks per run presented during either the ITI (unpredictable) or cue (predictable) periods.

Sub-study 3, NPU task: There will be 1 pre-TMS and 1 post-TMS NPU run during each TMS visit. Within each run, there will be 8 blocks (2 predictable, 2 unpredictable, 4 neutral). There are twice the number of neutral blocks to ensure that safe blocks alternate

with threat (predictable or unpredictable) blocks. Startle probes will be presented either during the cue period, or the ITI. During the predictable and unpredictable blocks, there will be 2 trials per condition. Given that there will be twice as many neutral blocks, during these blocks there will only be 1 trial per condition. The result will be a total of 192 trials across the entire experiment (2 [active vs. sham] x 3 [neutral vs. predictable vs. unpredictable] x 2 [maintenance vs. ITI] x 2 [pre-TMS vs. post-TMS] x 8 [block*trial repetitions]). There will be a total of 3 shocks per run presented during either the ITI (unpredictable) or cue (predictable) periods.

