Subjects will be informed that they can withdraw from the study whenever they wish. Sample shocks will be administered prior to the study. At this point, subjects will be explicitly asked if they wish to continue. Subjects receiving the frontal TMS will also be given a chance to experience the sensation of the TMS via electric scalp stimulation. Subjects will be given the opportunity to discontinue after this sensation screen. The experiment will also be stopped for any subject who exhibits signs of distress during any phase of the study. Subjects will be constantly monitored via closed circuit video by the AI for MRI sessions. An AI is present during TMS sessions. A credentialed staff member (RN, NP or MD) will assess the subject at the conclusion of the study or at any time if significant side effects develop. The subject will be withdrawn at any time if unable to follow the rules for participation in this study.

9. Outcome Measures

a. Primary outcome measures

The primary outcome measures will be APS reduction as a function of stimulation type, active or sham stimulation.

10. Statistical Analysis

a. Analysis of data/ study outcomes

Sternberg. APS scores will be created by subtracting the startle magnitude during the safe blocks from the startle magnitude during the threat blocks. These scores will be analyzed using a 2 [block: active vs. sham] x 2 [stimulation: TMS vs. no TMS] x 2 [interval: maintenance vs. ITI] repeated measures ANOVA.

NPU. APS scores for the cue and ITI will be created by subtracting the startle magnitude during the safe blocks from the startle magnitude during the unpredictable blocks. FPS scores will be calculated by subtracting the startle magnitude during the predictable ITI from the startle magnitude from the predictable cue. These scores (APS cue, APS ITI, FPS cue) will be analyzed using a 2 [block: active vs. sham] x 2 [stimulation: TMS vs. no TMS] repeated measures ANOVA.

b. Power analysis

In our Sternberg pilot experiment, we obtained the effect size ($f=0.72$) for our observed WM load-related decrease in anxiety. Assuming a somewhat smaller effect size ($f=0.5$) due to regression to the mean, if we set power at .95 and experiment-wise, two-tailed alpha at 0.05. Based on these parameters, we will need 48 subjects per experiment. Assuming a 15% unusable data rate and 3 subjects to initially adjust the experimental procedure, we will need 58 subjects per experiment.

11. Human Subjects Protection

a. Subject selection

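### The primary NPU outcome is not fixed to one score: section 10.a makes a cue and an ITI version of APS, adds FPS, and ranks none of them

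*Combined protocol and SAP*

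**What the plan says.** Four places in the combined protocol and SAP bear on the NPU outcome.

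- **Précis, Outcome measures.** The primary outcome for both tasks is "anxiety-potentiated startle (APS), which is the increase in startle magnitude during periods of threat compared to periods of safety". No threat type or measurement period is given.
- **Section 1.a, Background.** The NPU task is said to measure fear at the predictable cue, and "anxiety (e.g., anxiety-potentiated startle) in the N, P, and U contexts (no-cue periods". This is a description and contains no subtraction.
- **Section 9.a.** APS reduction, active against sham, is primary. Cue, ITI and threat type are not mentioned.
- **Section 10.a, NPU.** Two APS scores are made, one at the cue and one at the ITI. The rule given for each is "subtracting the startle magnitude during the safe blocks from the startle magnitude during the unpredictable blocks". FPS is the predictable cue minus the predictable ITI. The three scores (APS cue, APS ITI, FPS cue) then go into the same form of repeated measures ANOVA, with no order among them.

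Section 10.b sets the two-tailed alpha at 0.05 experiment-wise. No section says how that level is shared among the three NPU scores.

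**The concern.** A reader who asks which number decides the NPU sub-studies gets no single answer. Section 10.a gives the only formula, but it produces two scores that both carry the name APS, and section 9.a makes APS primary without choosing between them. Section 1.a points to the no-cue score; section 10.a gives the cue score equal standing.

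Two things are at stake. If either APS score (or FPS) may support the claim, the false-positive rate for the experiment exceeds the level in section 10.b. And if TMS affects startle in one period only, the cue and ITI scores will give different answers, and the plan does not say which one counts.

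**Working it through.** **The plan's own figure.** No figure in the documents depends on the choice of score. The nearest is n=48 per experiment (section 10.b: f=0.5, power 0.95, two-tailed 0.05). No test or correlation is given there, and the standard variants tried did not return 48. A one-degree-of-freedom paired test with a standardised difference of 0.5 needs 54 and has power 0.924 at 48. That is a separate matter. Only n=48 and alpha 0.05 are carried forward.

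**The places side by side.** *Safe* is read as the matched neutral period, which section 10.a does not spell out.

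| Place | Unpredictable ITI | Unpredictable cue | Predictable cue |
|---|---|---|---|
| Précis and 9.a | not specified | not specified | not specified |
| 1.a | anxiety | outside the no-cue periods | fear |
| 10.a | APS | APS | FPS |

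Sections 1.a and 10.a agree that unpredictable ITI measures anxiety and that the predictable cue measures fear. They differ on the unpredictable cue.

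**False-positive rate.** Inputs: n=48, no true effect, one two-sided test per score at 0.05 (the 2 x 2 ANOVA offers more than one effect per score, so this is the lenient count). The correlation between scores is not in the documents; 0 to 0.5 is assumed.

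- Independent scores: 1 − 0.95² = 0.0975 for the two APS scores; 1 − 0.95³ = 0.143 for all three.
- Correlation 0.5, by simulation of one-sample t-tests: about 0.09 for two and 0.13 for three.

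**Disagreement between the scores.** Assumptions: each active-minus-sham score has SD 1, the true effect is 0.5 SD where present, and the correlation between the cue and ITI scores is 0.3. The SD of their average is √((1 + 0.3)/2) = 0.806. Power is from the noncentral t at n=48.

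| TMS acts on | ITI score | Cue score | Average of the two |
|---|---|---|---|
| Unpredictable ITI only | 0.50, power 0.92 | 0, rejection rate 0.05 | 0.25; 0.25/0.806 = 0.310, power 0.56 |
| Cue and ITI equally | 0.50, power 0.92 | 0.50, power 0.92 | 0.50; 0.50/0.806 = 0.620, power 0.99 |

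At correlation 0.5 the SD of the average is √(1.5/2) = 0.866. The last column becomes 0.25/0.866 = 0.289 (power 0.50) and 0.50/0.866 = 0.577 (power 0.97).

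If the effect is equal in all threat cells, every version of the score estimates the same quantity and only precision differs.

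**The case against.** The strongest reply is that section 10.a is the analysis plan and the other wordings are summary or background. The Précis sentence has to fit the Sternberg task as well, which has one kind of threat. Section 1.a lists the neutral context alongside the two threat contexts, so it names settings and not cells to be averaged. The documents also give reason to expect cue and ITI to behave alike under unpredictable threat: section 4.d says the cue has no signal value there, and section 1.c reports raised startle at both. All of this stands. It does not settle which of the two APS scores is primary. If the plural in section 9.a's wording is taken to mean that both are, the alpha is still not divided.

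A reader might go further and infer that fear at the predictable cue leaks into the anxiety score. That comes from joining the Précis sentence to the remark in section 4.d that "safe blocks alternate with threat (predictable or unpredictable) blocks". The remark explains block order and the number of neutral blocks, not scoring, and section 10.a sends the predictable cue to FPS.

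A reader might also infer that the estimate changes two- to four-fold with the definition. That needs TMS to act on selected cells only. The documents give no cell means or SDs, and with an equal effect in all cells the ratio is 1.

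Nor do the documents support saying that sub-studies 2 and 3 could reach different conclusions from the same data. They are separate experiments: one uses 1 Hz stimulation of the left IPS during the task, the other 10 Hz offline stimulation with NPU runs before and after it.

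**Conclusion.** The point holds as one of ranking and wording. The plan has a usable NPU formula, but it yields two APS scores and FPS with no primary among them, while a single experiment-wise alpha of 0.05 is claimed. Tested at 0.05 each, the two APS scores carry a false-positive chance of about 0.09 to 0.10, and all three about 0.13 to 0.14. These figures rest on n=48, one test per score and an assumed correlation of 0 to 0.5.

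Whether the choice also moves the estimate depends on where TMS acts, which the documents do not establish. It could matter a good deal (power 0.92, 0.56 or a rejection rate of 0.05 if only the unpredictable ITI is affected), or it could leave the estimate unchanged. It should be settled before the data are analysed.

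**What to change.** In sections 9.a and 10.a, name unpredictable ITI minus neutral ITI as the single primary APS score for the NPU sub-studies. It is the contrast that fits both section 1.a and section 10.a. Make unpredictable cue minus neutral cue, and FPS, secondary. In the Précis, state that for the NPU task threat in APS means unpredictable blocks, and refer to section 10.a.

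The cost is wording only; no procedure or data collection changes. The cue score loses primary standing. If TMS acts equally at cue and ITI, the ITI score alone has power 0.92 where an average of the two, which the plan does not itself specify, would have 0.99 (effect 0.5 SD, correlation 0.3, n=48).

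If the investigators prefer to keep both APS scores primary, the plan should say so and divide the alpha. At 0.025 each, power for an effect of 0.5 SD on one score is 0.87 at n=48.

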ITI = intertrial interval
MEP = motor evoked potential
MRI = magnetic resonance imaging
MT = motor threshold
N = no threat
NPU = Threat test with neutral, predictable, and unpredictable conditions
P = predictable threat
rTMS = repetitive transcranial magnetic stimulation
TASS = TMS Adult Safety Screen
TMS = transcranial magnetic stimulation
U = unpredictable threat
WM = working memory

1. Introduction and Background

a. Background

The relationship between cognition and anxiety is complex and bidirectional (Robinson et al., 2013b; Vytal et al., 2012, 2013). Difficult tasks typically reduce anxiety, but performance on these tasks can suffer when individuals are in an anxious state. The mechanisms behind this bidirectional relationship are not yet known. Indeed, most prominent theories on the relationship between anxiety and cognition focus on the effect of anxiety on cognition, and largely ignore the effect of cognition on anxiety (Eysenck et al., 2007). As a result, the mechanisms underlying the reduction in anxiety during cognitive tasks remain largely unexplored. A better understanding of mechanisms involved in anxiety down regulation has clinical implications. For instance, individuals with anxiety disorders frequently suffer from attentional problems, such as being easily distracted and unable to focus on ongoing tasks. In fact, one of the core symptoms of generalized anxiety disorder (GAD) is “difficulty concentrating”(American Psychiatric Association, 2013). Such susceptibility to distraction has been linked to competition between task-relevant and task-irrelevant (e.g., worry) thoughts in working memory (WM) (Eysenck et al., 2007). To study this relationship in healthy subjects, it is possible to experimentally induce anxiety using the threat of shock paradigm.

Threat of shock is a well-validated ([name] and Ameli, 1998; Lang et al., 1990), translational procedure ([name], 2008a; [name] et al., 1994; Morgan et al., 1995; Robinson et al., 2012b), previously shown to increase state anxiety (Dunning et al., 2013; Hansen et al., 2009; Robinson et al., 2013b; Vytal et al., 2014), cause worry ([name], 2002, 2008b), and interfere with task performance (Balderston et al., 2015; Clarke and Johnstone, 2013; Lavric et al., 2003; Robinson et al., 2011, 2013a). In a typical threat of shock experiment, subjects are exposed to alternating blocks in which they are safe, or at risk for receiving an unpleasant electrical stimulation. Because the shock can be delivered infrequently, it is possible to superimpose a wide variety of tasks onto these alternating blocks, with little interference from the actual shock presentations, making this paradigm ideal for experimentally testing the effects of anxiety on cognitive processes, and their underlying neural mechanisms.

It is clear from resting state studies that threat of shock changes patterns of functional connectivity even in the absence of a cognitive task (McMenamin et al., 2014; McMenamin and Pessoa, 2015; Robinson et al., 2012a), and our data suggest that these resting state changes may be most robust in parietal regions of the frontoparietal attention network (FPN), potentially reflecting a state of threat induced hypervigilance (Balderston et al., 2017). Therefore, successful performance of a task during this altered baseline state may require additional cognitive control, when compared to non-threat periods. One candidate region that may be involved in this implicit emotion regulation is the dorsolateral prefrontal cortex (dlPFC). Indeed, the dlPFC has been repeatedly shown to play a role in WM (Altamura et al., 2007; Barbey et al., 2013; Curtis and D’Esposito, 2003; Feredoes et al., 2011; Geier et al., 2007), anxiety (Bishop, 2009; Forster et al., 2015; Nitschke et al., 2006; Peers et al., 2013; Shang et al., 2014), and emotional learning

(Carter et al., 2006). Studies with high anxious healthy controls have also implicated the dlPFC in anxiety/task interactions (Basten et al., 2011, 2012; Bishop, 2009; Eysenck et al., 2007; Fales et al., 2008; Telzer et al., 2008). In our pilot work, we show that even low load tasks activate the dlPFC under threat of shock, but that this activity is increased as cognitive load is increased.

Together these results suggest that the FPN plays a key role in the interaction between anxiety and cognition, however the nature of this role is unclear. We propose a novel model based on the frontoparietal attention network (FPN)²⁷. According to our model, 1) elevated state anxiety enhances bottom-up attentional processes, mediated by the parietal cortex, and 2) top-down cognitive control processes, mediated by the right dlPFC, counteract this enhancement, reducing anxiety. This model is an extension and integration of the arousal theory of parietal cortex asymmetry, which states asymmetries in parietal activity reflect arousal processes²⁸, and the attention control theory, which states that anxious individuals cannot efficiently engage goal-directed attention²⁹. Importantly, this model can be experimentally tested using TMS. TMS to the dlPFC was recently approved by the FDA as a second-line treatment for depression (Horvath et al., 2010; O'Reardon et al., 2007; Shajahan et al., 2002; Stern et al., 2007), and some studies have shown that TMS can reduce comorbid symptoms of anxiety in depressed individuals (Mantovani et al., 2013; O'Reardon et al., 2007; White and Tavakoli, 2015). TMS uses a strong magnetic current at the scalp to induce electrical currents in neurons just below the TMS coil. rTMS is capable of altering the resting membrane potentials of local neurons (Lefaucheur et al., 2014). rTMS at low frequencies (<5 Hz) tends to decrease local excitability, while rTMS at high frequencies (>5 Hz) tends to increase local excitability (Di Lazzaro et al., 2011). Therefore, 5 Hz rTMS should facilitate dlPFC activity, and according to our hypothesis this dlPFC stimulation in the absence of a task should inhibit threat-related processing, resulting in an overall decrease in anxiety.

One variant of the threat of shock paradigm is the so-called NPU paradigm, where subjects are exposed to simple cues during blocks of no threat (N), predictable threat (P), and unpredictable threat (U) (Schmitz and [name], 2012). During this paradigm, simple geometric shapes serve as cues (presented for 8 s). During the predictable threat blocks, these cues indicate that a shock may occur, while during the unpredictable and neutral blocks, these cues are not predictive of the shock. During the no threat blocks subjects are instructed that they are completely safe from shocks, and during the unpredictable blocks, subjects are instructed that they could receive a shock at any point. This paradigm provides measures of fear (e.g., fear-potentiated startle) associated with the threat cue in the P condition and of anxiety (e.g., anxiety-potentiated startle) in the N, P, and U contexts (no-cue periods). This paradigm is ideal to test the top-down inhibition hypothesis because it allows for the testing of both fear and anxiety, without adding additional cognitive demands. In addition, cue presentations during the NPU task activate the dlPFC (See below), which may reflect an implicit form of top-down emotion regulation.

The purpose of this protocol is to use TMS to determine the role of the FPN in anxiety reduction. According to our model, we have 2 hypotheses. First, suppressing activity in

the left parietal cortex with low frequency (1 Hz) rTMS should interfere with the bottom-up attentional processes associated with elevated state anxiety. Second, enhancing activity in the right dlPFC with high-frequency (10 Hz) rTMS should facilitate top-down cognitive control processes associated with anxiety reduction. Therefore the objective of this protocol is to test these hypotheses by altering FPN activity using non-invasive TMS, and measuring the effect of this altered FPN activity on anxiety using anxiety-potentiated startle (APS). Importantly, according to the top-down inhibition hypothesis strengthening activity the dlPFC with TMS alone (i.e. in the absence of a demanding cognitive task) should be sufficient to reduce anxiety, suggesting that we should see an effect in a passive task like the NPU paradigm. This is based on the following logic: 1) the dlPFC plays a key role in attention control (Basten et al., 2012; Cieslik et al., 2013; Fales et al., 2008; Harding et al., 2015; Peers et al., 2013), 2) anxiety patients are impaired in their ability to recruit this structure for cognitive control (Armstrong et al., 2011; Balderston et al., 2016b; Berggren and Derakshan, 2013a, 2013b; Braver et al., 2010; Coombes et al., 2009; Derryberry and Reed, 2002; Eysenck et al., 2007; [name] et al., 2015b; Morrison and Heimberg, 2013; Najmi et al., 2012, 2014; Price et al., 2011; Reinholdt-Dunne et al., 2009, 2012). 3) cognitive tasks that occur during periods of elevated state anxiety recruit the right dlPFC (See Preliminary Results), 4) tasks that engage the right dlPFC reduce state anxiety (Balderston et al., 2016a; Vytal et al., 2012, 2013). However, it is possible that some level of prior engagement of the stimulation site is necessary for the stimulation to be effective (Luber et al., 2007, 2008, 2013). Therefore we will test the effect of TMS on two outcome measures: 1) Fear and anxiety during the NPU task, and 2) Working memory (WM) related decreases in anxiety during the Sternberg WM task.

b. Significance

Anxiety disorders affect approximately 18% of the population in a given 1 year period, placing a substantial burden on the national health care system (Kessler and Chiu, 2005). Anxiety patients suffer from cognitive deficits, which can severely impact their wellbeing (American Psychiatric Association, 2013). We have shown that these deficits seem to be a core feature of anxiety disorders, and that they may be mediated by impaired FPN functioning (Balderston et al., 2016b). The purpose of this project is to determine whether noninvasive stimulation of the FPN can reduce anxiety. Given that TMS is already approved by the FDA for treatment of depression, these results may provide a potential avenue for future treatment of anxiety disorders.

c. Preliminary data

The NPU threat test provides reliable measures of both fear and anxiety. In order to understand the relationship between anxiety and cognition, it is important to have a reliable method for experimentally manipulating state anxiety independent of cognitive tasks. Our lab has repeatedly done this using the NPU threat test (Alvarez et al., 2011; Davis et al., 2010; [name] et al., 1994, 1998, 2004, 2006, 2008, 2011, 2012, 2015a; Robinson et al., 2012b; Schmitz et al., 2011; Schmitz and [name], 2012). As mentioned above, the NPU threat test consists of blocks of neutral, predictable, and unpredictable

threats. During this task, subjects are presented with cues, and these cues signal the shock only in the predictable conditions. Consistent with our previous work, our current pilot data show that this task can differentiate between fear and anxiety at both the psychophysiological and the neural level. At the psychophysiological level, subjects show elevated startle to the cue compared to the ITI during the predictable condition, and elevated startle during both the cue and ITI in the unpredictable condition (Figure 1).

[figure not shown]

Figure 1: Typical pattern of startle data in the NPU paradigm

At the neural level, cues evoke an fMRI pattern of activity consistent with fear in the predictable but not the unpredictable condition (Figures 2-3). Importantly, cues during both the predictable and unpredictable conditions evoke activity in the dlPFC, a region important for cognitive control (See below).

predictable > neutral

[figure not shown]

Figure 2: Cues in the predictable condition evoke neural activity in the fear network (dACC, anterior insula, thalamus).

unpredictable > neutral

[figure not shown]

Figure 3: Cues in the unpredictable condition fail to evoke neural activity in the fear network.

Anxiety is reduced by WM load in the N-back WM paradigm: In our initial studies exploring the relationship between cognition and anxiety, we conducted the n-back task under threat of shock. In a typical n-back experiment, subjects are required to continuously monitor a series of item, and make judgments on each trial according to whether the current item matches that presented “N” trials previously. Increasing “N” increases the number of items a subject is required to maintain in WM, and therefore the cognitive load placed on the subject. In our n-back studies we found that threat reduces performance on this task under low load conditions (Figure 4). In addition, we found that under high load conditions, anxiety, as probed with the startle reflex (anxiety-potentiated startle or APS) was reduced (Figure 5). Because the n-back task is complex and involves

various cognitive processes, it is unclear which mechanism is responsible for the anxiety reduction at high loads in this task. Indeed, the n-back task is highly dependent on executive function, requiring simultaneous encoding, maintenance, and retrieval (Kane et al., 2007; Owen et al., 2005). Furthermore, during the 2- and 3-back task, subjects must also shift their attention away from representations of the intermediate to-be-maintained items, further engaging prefrontal cognitive control resources.

[figure not shown]

Figure 4: Threat reduces accuracy during verbal n-back task.

Figure 5: APS is reduced during 3-back relative to view condition.

Anxiety is reduced by WM load in the Sternberg WM paradigm: Therefore, in an effort to better understand the psychological mechanisms underlying the load related anxiety reduction, we followed up the N-back studies with the Sternberg WM paradigm (Sternberg, 1966). In the Sternberg WM paradigm, subjects are presented with a series of letters, and required to maintain this series of letters in WM for a brief maintenance interval. After the maintenance interval, subjects are presented with a response prompt, which consists of a letter and a number. The letter is chosen from the study series, and the number corresponds to a position in the series. At the prompt, subjects are instructed to identify whether the position of the letter in the series matches the number. By varying the number of to-be-encoded letters in a series, it is possible to increase WM load. Because simple rehearsal is sufficient to maintain these letters (Altamura et al., 2007), this task does not require the engagement of central executive resources (Baddeley, 1992).

In these follow-up studies, we required subjects to perform the Sternberg task during periods of safety and threat. We increased WM load by manipulating the number of letters in this series, and probed subjects anxiety with the startle reflex during the safe or threat blocks. Consistent with the previous n-back studies, we found that increasing WM load reduces anxiety (APS), when anxiety is probed during the maintenance period, but not the ITI (Figure 7). This is true even though the Sternberg task typically does not engage central executive processes, suggesting that this acute anxiety down-regulation can be caused by WM components other than the central executive. However, unlike the previous n-back studies, performance was not impaired under threat of shock (Figure 6), suggesting that the central executive processes, rather than maintenance processes were impacted by anxiety in the n-back task.

[figure not shown]

Figure 6: Sternberg WM performance is not affected by threat.

Figure 7: APS is reduced during the maintenance period of high load Sternberg WM trials.

Threat of shock activates the dlPFC: In addition, in several recent studies we found that threat of shock evoked activity in the dlPFC. In Study 1 (n = 37), subjects completed the NPU task. In Study 2 (n = 36), subjects underwent an incidental picture encoding session, where pictures of common household items were presented during blocks of safety and (unpredictable) threat. Subjects were simply instructed to indicate whether the item presented on each trial could typically be found inside a house or outside a house. In Study 3 (n = 21), subjects completed maintenance and manipulation trials in the Sternberg working memory paradigm. On each trial, subjects were presented with a series of letters, followed by a brief maintenance interval, followed by a response prompt. On maintenance trials, subjects were instructed to maintain the series of letters in working memory in their current order. On manipulation trials, subjects were instructed to sort the trials in alphabetical order. In all studies we found a significant cluster of activity over the right dorsolateral prefrontal cortex (dlPFC) as a function of threat. Across studies this region showed increased cue-evoked activity during threat blocks relative to safe blocks (Figures 8-10).

[figure not shown]

Figure 8: Increased cue-evoked activity during unpredictable vs. neutral periods in the NPU task.

Figure 9: Increased activity during threat compared to safe in a picture encoding task.

Figure 10: Increased activity during threat compared to safe in the Sternberg WM task.

Anxiety patients show impaired performance and dlPFC activity during N-back: In a recent study we sought to determine whether WM-related deficits in clinical anxiety are chronic, or whether they arise due to threat-related processing (e.g. worry). In the latter case, one would expect that experimentally-inducing threat would exacerbate the deficits in anxiety patients. We tested WM performance during threat of shock and safety in anxiety patients and healthy controls, while recording brain activity with functional magnetic resonance imaging (fMRI). Subjects performed a spatial N-back working memory (WM) task comprising 4 levels of difficulty (i.e., cognitive load), 0-back, 1-back, 2-back and 3-back conditions. In this study we found that patients were impaired

relative to controls across all levels of the N-back task, and that this performance impairment was independent of the threat manipulation (Figure 11). Similarly, the task-positive BOLD activity in the dIPFC was reduced in patients relative to controls (Figure 12). These results suggest that poor engagement of the prefrontal cortex (particularly dIPFC) in clinical anxiety reflects a core component of the disorder rather than a transient effect of threat-related processing (Basten et al., 2011; Bishop, 2009; Telzer et al., 2008).

[figure not shown]

Figure 11: Anxiety patients show reduced accuracy and increased RT during N-back task.

[figure not shown]

Figure 12: Anxiety patients show reduced WM related dIPFC activity.

Threat of shock fundamentally alters the IPS. In two recent studies, we exposed subjects to threat of shock while recording brain activity using MEG or fMRI (See Figure 2). In the MEG study, subjects received startle probes, and we sampled the MEG activity during the 2 seconds prior to the probe. When we compared the power from safe blocks to the power from threat blocks using a paired-sample t-test, we found a significant decrease in power during the threat blocks compared to the safe blocks in the alpha band over parietal sensors, suggesting an increase in cortical excitability (Klimesch et al., 2007). We used a beamformer to localize the source of this power decrease, and found a large cluster of voxels in the IPS showing a decrease in alpha power in the threat blocks compared to the safe blocks.

In the fMRI study, we assessed functional connectivity during threat blocks vs. safe blocks using the whole brain global brain connectivity (GBC) approach. This allowed us to assess functional connectivity from threat to safe across the entire brain, without specifying a seed-region. This approach allows us to identify the regions of the brain that show the most significant changes in connectivity with the rest of the brain as a function of our task design, and has previously been used to identify network hubs at the whole-brain level (Cole et al., 2010). We found a significant increase in GBC in the threat blocks compared to the safe blocks bilaterally in the IPS, showing that this region increased its connectivity with the rest of the brain during threat blocks, suggesting that this region functions as a network hub for threat-related attentional processes.

TMS pulses evoke transient eyeblink responses due to stimulation of the scalp: In a recent pilot, we tested the effect of TMS pulses on eyeblink responses. Given that our primary outcome measure is startle, we wanted to ensure that stimulation of the scalp muscles did not interfere with our ability to record startle evoked eyeblinks. We found that TMS pulses (in a 5 Hz train) indeed induce twitches in the orbicularis oculi muscle. However, these twitches were small, and the EMG signal recovered within 150 ms of the TMS pulse (See Figure 13). When comparing the TMS evoked eyeblink to the acoustic startle reflex, it is clear that the TMS evoked eyeblink has an earlier onset, and a shorter duration than the acoustic startle reflex. This difference is likely due to the origin of the two blinks. The TMS evoked blink arises due to direct stimulation of the orbicularis

oculi, while the blink evoked by the startle probe arises through the CNS via engagement of the acoustic startle reflex arc (Blumenthal et al., 2005).

